Official Title of the study: Project Impact: An Innovative Approach to Weight Loss Maintenance NCT number: NCT02363010 Date of the document: August 1, 2020

Design and Randomization

This study was a three-arm, randomized controlled trial. The study was approved and monitored by the Drexel University institutional review board and preregistered at clinicaltrials.gov (Clinical Trials Identifier: NCT02363010). Participants provided informed consent during enrollment, which was conducted by the research coordinator and research assistants. The statistician conducted randomization using a random numbers table. Participants, counselors, and other study staff were blind to allocation, with no access to allocation data during Phase I. During Phase II, three different forms of behavioral treatment were tested and only outcomes assessors remained blinded to condition. An independent officer completed data and safety monitoring.

Participants

Participants were recruited from the community for this study from 2014 to 2016. Inclusion criteria were: BMI 27 – 45 kg/m² (measured in clinic), age 18-70 years, and completion of all steps in the enrollment process. Exclusion criteria were: medical or psychiatric conditions that could pose a risk during lifestyle modification or significantly limit the ability to begin a program of PA; history of bariatric surgery; current use of weight-affecting medication; weight loss of 5% or more in the past 6 months; current pregnancy, lactation, or plans to become pregnant during the study period; participation in or plan to participate in another weight loss program during the study period; having an immediate family member or household member participating in the study. Participants received compensation for assessment visits as follows: \$25 for baseline, \$25 for month 6, \$25 for month 12, and \$50 for month 18.

During project planning, estimates of the necessary sample size varied from 300 to 350, depending on attrition. At project launch, a final sample of 320 participants was selected, with

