the assumption of up to 30% attrition, to provide 81% power to detect a medium effect size of weight loss or MVPA. Power analyses accounted for a three-level hierarchical structure, with repeated measures for each participant in a group within one of the three intervention arms, assuming a within-subject correlation of 0.5 and a within-group correlation of 0.05 (estimated from pilot data). A medium effect size was chosen because 1) an effect of that size may be needed to justify a departure from standard behavioral treatment (McGough & Faraone, 2009), 2) previous research comparing ABT to BT has observed a medium effect size for a primary outcome (Forman et al., 2016), and 3) medium or larger effect sizes have been observed for the comparison of weight loss in those engaging in high versus low MVPA (Tate, Jeffery,

Sherwood, & Wing, 2007).

Shared Intervention Components

Phase I (Months 1 to 6) consisted of 16 closed-group sessions, held on a weekly (8 sessions) and then bi-weekly (8 sessions) basis, with approximately 12 participants in each group. During Phase I, all participants received BWL treatment designed to induce 10% weight loss, with materials adapted from Look AHEAD (2006) and the Diabetes Prevention Program (2002). Participants were instructed to keep daily records of dietary intake. Calorie intake was emphasized as the key determinant of weight loss. Stimulus control, problem solving, goal setting, and social support skills were taught. Participants were instructed to gradually self-monitor and increase free-living MVPA, with a goal of maintaining 250 minutes per week of MVPA by 6 months and beyond. Participants were instructed to conduct MVPA in bouts of 10 minutes or more. Participants self-reported weekly MVPA minutes and average calorie intake during each session's group check-in, and counselors also provided brief written feedback on self-monitoring records on which exercise and dietary intake were reported. Counselors had

doctoral-level psychology training. In Phase I and II, all group sessions began with private measurement of weight.

Phase II Interventions (Months 7-18)

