The amount of emphasis on promoting PA was designed to be similar in BT+PA and ABT+PA. However, in ABT+PA, acceptance-based behavioral skills were taught, rather than traditional behavioral skills. This approach was adapted primarily from an acceptance-based weight loss protocol (Forman & Butryn, 2016). A key goal was to increase awareness of internal experiences that shape PA behaviors. The approach validated the sense that many aspects of PA are "uncomfortable," meaning that it can be difficult to tolerate the thoughts (e.g., "I would rather be doing something else"), emotions (e.g., boredom), urges (e.g., to avoid or end exercise), or physical sensations (e.g., sweating) that occur while one attempts to engage in PA or while making PA-related decisions. Participants learned how to respond to internal experiences with a stance of non-judgmental acceptance, which enables flexibility (i.e., the ability to engage in a wide range of behaviors, regardless of the accompanying internal experiences). Ultimately, acceptance was intended to promote long-term persistence in PA. Values clarity, which is integral to the use of acceptance skills, included the ability to consider the ways in which being physically active enables pursuit of what is most important in one's life (e.g., being physical fit can make travel or community service more feasible). Participants were encouraged to use their "long-term mind" to have a heightened awareness of their values at moments of PA-related decision making, rather than being driven by transient internal experiences.

Measures

Assessments were conducted at Months 0, 6, 12, and 18.

Demographics. Race, ethnicity, sex, age, and education were self-reported at baseline.

Moderate-to-Vigorous Physical Activity. Participants were instructed to wear ActiGraph (Pensacola, FL) GT3X tri-axial, solid state accelerometers for all waking hours for 7 consecutive days at each assessment point. ActiLife software was used with cutpoints defined by Troiano et al. (2008) to identify bouts of 10 minutes or more in which PA of moderate-to-vigorous intensity was detected. Data were considered valid and included in data analyses if the participant wore the accelerometer for at least 10 hours each day for 4 or more days.

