Data were analyzed in R (Team, 2013) and SPSS Version 25 (IBM Corp., 2017). Data distributions and assumptions were examined before conducting any formal statistical test. Analyses were conducted on an intent-to-treat basis with multiple imputation via the mice package in R (van Buuren, 2011), such that all participants enrolled in the trial were included in analyses (BT: n = 110, BT-PA: n = 105, ABT-PA: n = 105), with two exceptions noted for exploratory analyses. We performed the analyses for each of the imputed datasets separately, and combined the test statistics across datasets based on Rubin's rule as implemented in the miceadds package in R (Robitzsch, 2017). To account for the zero-inflated distribution of MVPA, compound Poisson linear regression models (cplm; Zhang, 2013) were used to test the treatment effect on MVPA at 12 and 18 months separately, controlling for MVPA measured at earlier time points. The effect of treatment on percent weight loss at 12 and 18 months were examined separately using general linear models controlling for weight measured at earlier time points. General linear models also were used to examine the treatment effect on half-mile walk time and waist circumference. Moderation analyses were used to examine whether the effect of treatment condition on MVPA or percent weight loss depended on sex, baseline BMI, baseline MVPA, weight loss in Phase I or change in MVPA during Phase I. Additional exploratory analyses using general linear models were performed to further understand the relationship between specific

levels of MVPA (regardless of condition) and weight loss outcomes among participants (n = 271) who provided data at 6 months; this subsample was chosen to reduce missing data to allow for greater precision in estimating dose-response for this analysis.

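### Months 12 and 18 are tested in separate models, so the plan has no estimate of whether an arm effect lasts, and its Month 18 adjustment, read literally, can imitate fading

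*Combined protocol and SAP*

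**What the plan says.** The power paragraph under Participants states: "Power analyses accounted for a three-level hierarchical structure, with repeated measures for each participant in a group within one of the three intervention arms". It assumes a within-subject correlation of 0.5 and a within-group correlation of 0.05, and gives the sizing basis as "the assumption of up to 30% attrition, to provide 81% power to detect a medium effect size of weight loss or MVPA".

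The section Data Analysis Plan: Results Through 18 Months uses compound Poisson models for MVPA "to test the treatment effect on MVPA at 12 and 18 months separately, controlling for MVPA measured at earlier time points". Likewise, the effects on "percent weight loss at 12 and 18 months were examined separately using general linear models", with weight at earlier visits as covariates. The section describes no joint longitudinal model, no effect pooled over Phase II and no arm-by-visit term. It does not list which visits count as earlier for each model.

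The trial's title names weight loss maintenance as its subject, and the description of ABT+PA says that "acceptance was intended to promote long-term persistence in PA".

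**The concern.** The sizing and the analysis use the visits differently. The sizing treats a participant's visits as repeated outcomes; the analysis takes one visit's outcome at a time and uses earlier visits only as covariates. Two things follow.

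First, no planned quantity compares the arm effect at Month 12 with that at Month 18. A reader who wants to know whether an effect lasted has only two separate results to set side by side. One significant and one non-significant result do not show that the effects differ.

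Second, both outcomes carry the same open wording about earlier visits. For the Month 18 model, taken literally, those visits include Month 12, which was measured during Phase II after the three treatments had separated. The arm coefficient at Month 18 is then the effect given Month 12 status, not the total effect of the arm at Month 18. A lasting effect already present at Month 12 is partly adjusted away.

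At stake is how a maintenance trial's main results are read: a steady effect could be reported as one that wanes.

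**Working it through.** **Inputs from the documents.** 320 participants and 30% attrition (Participants): 320/3 × 0.7 = 74.7 per arm. Within-subject correlation ρ = 0.5 and within-group correlation 0.05 (same section). Groups of about 12 (Shared Intervention Components): design effect (DE) 1 + 11 × 0.05 = 1.55, or 1 + 7.4 × 0.05 = 1.37 if attrition thins groups to 8.4.

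**Assumptions, because the documents are silent.** Medium effect taken as d = 0.5 between two arms; two-sided 5%; equal correlation between all visits; MVPA treated as normal. Power = Φ(d / √(2·V·DE/n) − 1.96), where V is the outcome variance in SD² units.

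**Step 1: the stated 81%.** For the unadjusted mean of two visits, V = (1 + 0.5)/2 = 0.75. With DE 1.55 the standard error is √(2 × 0.75 × 1.55/74.7) = 0.176, and 0.5/0.176 = 2.83, so power is 80.9%. The figure reproduces, but not uniquely: one visit adjusted for one earlier visit has V = 1 − 0.5² = 0.75 and gives the same 80.9%. One unadjusted visit (V = 1) gives 68.9%.

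**Step 2: one visit, adjusted for Months 0 and 6.** V = 1 − 2ρ²/(1 + ρ) = 0.667. Power is 85.2% (DE 1.55) or 89.2% (DE 1.37).

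**Step 3: both visits averaged, same covariates.** The conditional covariance is ρ − 2ρ²/(1 + ρ) = 0.167, so V = (0.667 + 0.167)/2 = 0.417.
- If DE multiplies V, the saving is 1 − 0.417/0.667 = 37.5%, and power rises to 96.7% (DE 1.55) or 98.1% (DE 1.37).
- If the group component is common to both visits and is not reduced by averaging (DE 1.37, so add 0.37), the variances are 1.037 and 0.787. The saving is 24%, and power goes from 85% to 93%.
- Adding 0.55 instead (12 per group) gives 1.217 and 0.967: a saving of 21% and one-visit power of 79%. That convention gives only 76% for the unadjusted two-visit mean in Step 1, so it does not reproduce the plan's 81%.

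**Step 4: apparent fading when the effect is constant (Months 0 and 6 as covariates).** The two visit estimates correlate 0.167/0.667 = 0.25. The chance of significance at Month 12 but not at Month 18 is P(Month 12) − P(both):
- d = 0.5: 0.852 − 0.741 = 11.1% (DE 1.55); 0.892 − 0.806 = 8.6% (DE 1.37).
- d = 0.35: about 20%.
- d = 0.35 with ρ = 0.8: 6–8%.

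The reverse pattern is equally likely. With the group component unreduced (DE 1.37), the three figures are about 9%, 16% and 10%.

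**Step 5: Month 12 also in the Month 18 model.** The coefficient of Month 12 given Months 0 and 6 is ρ/(1 + 2ρ) = 0.25, so the arm coefficient is 0.50 × (1 − 0.25) = 0.375. A 4,000-run simulation without clustering gave 0.377. The residual variance is 1 − 3ρ²/(1 + 2ρ) = 0.625. Power at Month 18 becomes 64.4% (DE 1.55) or 69.7% (DE 1.37). The false-fade pattern rises to 0.852 × (1 − 0.644), about 30%, or 0.892 × (1 − 0.697) = 27%. For ρ from 0.3 to 0.8 the coefficient runs from 0.406 to 0.346.

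**The case against.** The strongest reply is that the planned tests are not weak. They are adjusted for earlier visits, and Step 2 puts them above 81%. This stands. A reader might infer that the trial is underpowered, or that the 81% belongs to no planned test. The documents support neither: the alpha, the numerical effect size and the number of repeats behind the 81% are not given, and an adjusted single-visit test reproduces it as well as a two-visit mean does. The 64–70% in Step 5 comes from the changed meaning of the Month 18 coefficient, not from testing the visits separately.

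A reader might also infer that the second visit contributes nothing. That is too strong. As a covariate, Month 12 lowers the Month 18 residual variance from 0.667 to 0.625, and it may inform the multiple imputation, whose predictors are not stated.

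Visit-specific effects are legitimate targets, Month 18 speaks directly to lasting benefit, and the plan states no rule that infers fading from two p-values. The persistence sentence is treatment rationale, not a hypothesis. All this is fair, and it limits the point to what the plan cannot estimate. But the total effect at Month 18 answers that question only if Month 12 is left out of its model, and the plan does not say so. The authors may have meant Months 0 and 6 only.

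Finally, the sizes depend on ρ, d and how clustering enters, so a 20% false-fade rate should not be quoted without its d = 0.35.

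**Conclusion.** The point holds in a limited form and should be addressed. The plan has no pooled Phase II effect and no arm-by-visit estimate, so it cannot distinguish a lasting effect from a fading one, and for a sustained effect it forgoes a variance saving of about 24–38% (ρ = 0.5, DE 1.37). Separate testing alone would make a constant effect look like a fade in about 9–11% of trials at d = 0.5. The more serious risk lies in the wording on earlier visits: if Month 12 enters the Month 18 model, a constant 0.50 SD effect shows as 0.375 SD and the false-fade rate is about 27–30%. No loss against the stated 81% is demonstrated.

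These sizes rest on d = 0.5, two-sided 5%, 74.7 per arm, equal correlations and a normal approximation for MVPA. The absence of a persistence estimate does not depend on them.

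**What to change.** Fit one model per outcome, with Months 12 and 18 as repeated outcomes, Months 0 and 6 as the only earlier-visit covariates, and arm, visit and arm-by-visit terms. State explicitly that Month 12 is not a covariate for Month 18. Allow for within-participant correlation by a random intercept or cluster-robust errors, and keep the compound Poisson family for MVPA. Fit the model in each imputed dataset and combine the results as already planned. Report both visit-specific effects, their average and their difference. Base any statement about persistence or fading on the arm-by-visit estimate and its interval. If results have already been reported, add this as a labelled supplementary analysis.

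The cost is plan wording and a modest amount of code; all the data are already scheduled for collection. The drawback is dilution when an effect exists at one visit only. With 0.5 SD at Month 12 and none at Month 18, the average effect is 0.25 SD and its power about 52%, against 89% for Month 12 alone (DE 1.37, Months 0 and 6 as covariates). For that reason the visit-specific estimates are kept beside the average.

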Group sessions (14 total) continued in Phase II, beginning with 7 weekly sessions followed by 4 bi-weekly sessions. The final three sessions were held in Months 12, 15, and 18. Each participant also had a 15-minute phone call with a counselor between the quarterly sessions (three calls total) to promote continued engagement. Supplementary Table A details the intervention content in each arm.

Behavioral Therapy (BT)

The BT condition in Phase II continued to be based on Look AHEAD (2006) and Diabetes Prevention Program (2002) materials. Sessions were designed to apply traditional behavioral skills such as problem solving and goal setting to the challenges of long-term lifestyle modification. Approximately two-thirds of intervention content and session time was designed to be applied to eating behavior, with a secondary emphasis on PA.

Behavioral Therapy with Physical Activity Emphasis (BT+PA)

In the BT+PA condition, approximately two-thirds of session time and content was designed to focus on PA, with one-third of session time focused on eating behavior. The intervention was created by adapting material from the Look AHEAD (2006) and Diabetes Prevention Program (2002) protocols to be PA-focused, and by incorporating techniques from Michie's behavior change taxonomy (Michie et al., 2011). For example, when a session on "maintaining motivation" was conducted, exercises and discussion in session were focused primarily on enhancing motivation for PA. As another example, the application of goal setting skills was primarily focused on PA goals. Progress towards PA goals, particularly the barriers or facilitators of such progress, was reviewed in each session in greater detail than occurred in the BT condition. PA, rather than eating behavior, was the primary target for problem solving skills. Group leaders frequently encouraged development of implementation intentions for PA.

Acceptance-Based Behavioral Therapy with Physical Activity Emphasis (ABT+PA)

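### The trial was sized for participants nested in treatment groups (ICC 0.05), but the outcome models as described have no group term; at a residual ICC of 0.05 a 5% pairwise test runs at about 9-12%.

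*Combined protocol and SAP*

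**What the plan says.** The sample-size text under Participants states: "Power analyses accounted for a three-level hierarchical structure, with repeated measures for each participant in a group within one of the three intervention arms". It assumes a within-subject correlation of 0.5 and "a within-group correlation of 0.05 (estimated from pilot data").

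Shared Intervention Components describes closed Phase I groups with "approximately 12 participants in each group". Under Phase II Interventions (Months 7-18), delivery stayed group-based: "Group sessions (14 total) continued in Phase II, beginning with 7 weekly sessions followed by 4 bi-weekly sessions", with three further sessions in Months 12, 15 and 18.

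Data Analysis Plan: Results Through 18 Months gives the models:

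- Percent weight loss: "The effect of treatment on percent weight loss at 12 and 18 months were examined separately using general linear models", adjusted for earlier weight.
- MVPA: compound Poisson regressions that "were used to test the treatment effect on MVPA at 12 and 18 months separately, controlling for MVPA measured at earlier time points".
- Other outcomes: "General linear models also were used to examine the treatment effect on half-mile walk time and waist circumference".
- Missing data: "Analyses were conducted on an intent-to-treat basis with multiple imputation via the mice package in R", with results pooled by Rubin's rules.

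The section names software, imputation method, pooling rule and covariates. It names no group effect, no mixed model and no cluster-robust variance, and it does not list the variables in the imputation model.

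**The concern.** People treated together in a closed group share a counselor, a group climate and each other's influence, so their outcomes tend to be correlated. The plan accepts this when it sizes the trial. A general linear or compound Poisson model without a group term treats all 320 participants as independent, so it understates the variance of every between-arm contrast whenever the residual group correlation is positive.

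Adjusting for earlier values is not a substitute. It removes only the group differences that those values already carry. The arm-specific treatments start after Month 6, so group divergence arising in Phase II is not captured by the Month 6 covariate.

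The main arm comparisons, MVPA and percent weight loss, are at stake, and by the same mechanism walk time and waist circumference. Intervals that are too narrow could change a borderline conclusion about departing from standard behavioral treatment, which is the decision the plan uses to justify its effect size.

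**Working it through.** **Inputs from the documents.** N = 320 (110/105/105); attrition up to 30%, so 320 × 0.70 = 224 completers; within-group correlation 0.05; within-subject correlation 0.5; about 12 per group in Phase I; stated power 81%; 271 participants with Month 6 data.

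**Assumptions not in the documents.** Two-sided 5% test; a medium effect means d = 0.5; Phase II group size m between 12 × 0.70 = 8.4 and 12; about 320/12 ≈ 27 groups.

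**Step 1: the stated power.** Completers per arm: 224/3 = 74.7. Design effect: 1 + (12 − 1) × 0.05 = 1.55. Variance factor from the repeated measure: 1 − 0.5² = 0.75. Effective n per arm: 74.7/(1.55 × 0.75) ≈ 64.2. Noncentrality: 0.5 × √(64.2/2) ≈ 2.83. Power: Φ(2.83 − 1.96) ≈ 80.9%, against the stated 81%. Other conventions also land near 81%, so this does not identify the sponsor's formula. It is consistent with clustering having been built in.

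**Step 2: true size of a test that ignores groups.** DE = 1 + (m − 1) × ICC. Pairwise size = 2 × [1 − Φ(1.96/√DE)]. Three-arm size = P(χ² on 2 df > 5.991/DE).

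| Residual ICC | DE (m = 8.4 / 12) | Pairwise | Three-arm |
|---|---|---|---|
| 0.01 | 1.07 / 1.11 | 5.9% / 6.3% | 6.2% / 6.7% |
| 0.02 | 1.15 / 1.22 | 6.7% / 7.6% | 7.4% / 8.6% |
| 0.05 | 1.37 / 1.55 | 9.4% / 11.5% | 11.2% / 14.5% |

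At 0.05 the standard error should be √1.37 = 1.17 to √1.55 = 1.25 times larger. A simulation of the ordinary three-arm linear model (40,000 runs, 9 groups per arm, ICC 0.05) gave 11.3-11.5% pairwise with 110/105/105 and 9.2-9.5% with 76/74/74. With no clustering it gave 4.8-5.0%.

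**Step 3: the described workflow.** Simulation with 27 groups of 12, individual correlation 0.5, missingness of 49/320 = 15.3% at Month 6 and 30% at Month 12, 10 imputations without group, covariate adjustment and Rubin pooling. Here 0.05 is the ICC of the outcome *before* adjustment.

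| Month 6 and 12 group effects | Residual ICC | Pairwise | Three-arm |
|---|---|---|---|
| None at Month 6 | 0.074 | 11.2% | 13.8% |
| Correlated 0.5 | 0.059 | 10.7% | 12.0% |
| Correlated 0.9 | 0.037 | 7.8% | 9.3% |

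Monte Carlo error is about 0.5-0.7 points; with ICC 0 the pairwise rate is 4.3%. A separate run of the pairwise simulation gave 10.5%, 10.1% and 8.0%, with 4.5% under no clustering. The residual ICC can exceed 0.05 because covariates remove individual variance faster than group variance.

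**Step 4: MVPA.** A compound Poisson simulation (index 1.5 and about 28% zeros, both assumed; no imputation; outcome ICC 0.05) gave 8.1% pairwise with 8 per group and 12.6% with 12, and 10.3-15.2% for three arms. At ICC 0.01-0.02 the pairwise rate is 6.2-7.7%. The model already runs at 5.4-5.8% with ICC 0, so not all of the excess is clustering. This simulation was run once and not repeated.

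**The case against.** The analysis section is a short summary in the past tense. It gives no full specification, so a group term may have been fitted and not reported. It lists no imputation variables at all, so the absence of group from that list tells us little. This stands as a limit on what can be inferred about the analysis actually run. It does not rescue the text, which contradicts the plan's own variance premise if followed as written. The general remark that assumptions were examined does not mention clustering.

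The stronger objection concerns size. The plan does not say whether 0.05 is an adjusted or an unadjusted ICC, and gives none for walk time or waist circumference. If the same groups ran through both phases, Month 6 values should carry some group effect, which makes the 11.2% scenario the least plausible. At Month 18, adjusting also for Month 12, group effects correlated 0.9 leave a residual ICC of about 0.025 and an error of 7-8%; correlated 0.5, the residual ICC stays near 0.054. If groups were re-formed for Phase II, neither the 12 per group nor the 27 groups carries over.

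Group-blind imputation also dilutes the correlation. At 12 per group the formula gives 14.6%, 12.7% and 9.8% for residual ICCs of 0.074, 0.059 and 0.037, against the simulated 11.2%, 10.7% and 7.8%. Interpolating, a residual ICC of 0.05 under that workflow gives roughly 9-10%, the lower part of the 9-12% range.

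Nor does the information fall to 27 units: the design effects imply an effective sample of 320/1.55 ≈ 206 to 320/1.37 ≈ 234. All of this bears on how large the inflation is. None of it removes the mismatch or changes its direction.

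**Conclusion.** The concern holds and must be fixed. The described outcome models omit a source of variance that the plan itself assumed, from its own pilot data, when it set the sample size.

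For a two-sided 5% test with 8.4-12 per group, the pairwise error is 9.4-11.5% at a residual ICC of 0.05, falling to 5.9-6.3% at 0.01. If 0.05 is instead the unadjusted ICC, the simulated workflow gives 7.8-11.2% at Month 12, with Month 18 tests toward the low end. "About double" is therefore a fair description only when the residual ICC is near 0.05.

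The direction, standard errors too small under positive residual correlation, depends on none of the assumed figures. The size for this trial cannot be settled from the documents, because they give neither the number and size of Phase II groups nor any observed ICC.

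**What to change.** For MVPA, percent weight loss, walk time and waist circumference, add a random intercept for treatment group, or use cluster-robust variance with a small-sample correction. Base degrees of freedom on the actual number of groups: about 27 − 3 = 24 if there were 27. Include the group identifier in the imputation model. Report the number and size of Phase II groups, whether Phase I groups were kept intact, and the estimated ICC for each outcome. If a group term was in fact fitted, say so and report the same quantities.

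In a check simulation, group-aware imputation with cluster-robust errors on 24 df gave 3.5-4.4%. Cluster-robust errors on group-blind imputation gave 3.9-6.8%, so correcting the variance matters most and group-aware imputation is the safer companion. That check was run once and not repeated.

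The cost is a re-run on data already held, plus SAP wording. Intervals widen by √DE × 2.064/1.968: about 23-31% at ICC 0.05 and 12-16% at ICC 0.02.

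Power for d = 0.5 with 224 completers, ICC 0.05 and 24 df, using variance 2 × (v_group × m + v_individual)/74.7:

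- 65-71% with no covariate gain (0.5/√(2 × 1.55/74.7) = 2.454 for m = 12; 2.610 for m = 8.4).
- 75-82% if covariates cut individual variance by one third.
- 82-87% only if they also cut group variance by one third.

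With 19 groups of 12 (16 df) these become about 64%, 73% and 81%. This loss of power is the price of a valid error rate, and should be stated alongside the revised results.
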